NSH 1432 PROTOCOL

TITLE

Continuous Monitoring Using a Smart Implantable Device to Compare Medial Parapatellar vs. Subvastus Approaches in Early Post-Operative Total Knee Arthroplasty Recovery

PRINCIPAL INVESTIGATOR

[name]

AUTHORS

[name], [name], [name],

SPONSOR

None

INTRODUCTION

Total knee arthroplasty (TKA) is a highly effective intervention for end-stage knee arthritis, with two common surgical approaches: the Medial Parapatellar (MPP) approach and the Subvastus (SV) approach. Both techniques demonstrate similar long-term outcomes (6 months and beyond) in terms of functional scores, range of motion (ROM), and patient satisfaction, as documented in numerous studies. A key limitation in the literature, however, is the lack of day-by-day data on functional recovery and gait parameters in the crucial first 30 days post operatively - an important period when patients are regaining independence and returning to daily activities.

Persona IQ (Zimmer Biomet) is an FDA-approved smart knee implant that captures continuous, real-world gait data (ROM, step count, stride length, walking speed, etc.) directly from the tibial implant. Unlike external wearables, PIQ provides objective, high-frequency metrics directly from the implant¹. By leveraging PIQ technology in combination with step-tracking wearables, this prospective study aims to fill the current gap by providing daily metrics about the patients pre-operatively and their recovery trajectories during the first 30 days post-operatively and correlating this data with standard PROMs. In this study, patients will be enrolled before surgery and followed longitudinally.

We hypothesize that the SV approach will demonstrate a quicker return to functional milestones in the early post-operative period compared to the MPP approach, even if long-term outcomes have no significant difference. Specifically, we anticipate improved gait metrics (ROM, step count, walking speed) and PROMs (KOOS Jr., NPRS & VR-12) from post-op day 1 to 30 in the SV group compared to the MPP group. The main primary outcome of this study will be step count. This study has the potential to enhance surgical decision-making and optimize rehabilitation protocols by identifying the approach that accelerates early functional recovery.

REVIEW OF LITERATURE

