Existing studies comparing MPP and SV approaches typically report outcomes at discrete time points - post-operative day 1, week 4, month 3, and beyond²⁻⁵. These studies consistently demonstrate no significant differences in functional outcomes at 3 or 6 months and beyond post operatively²⁻⁹. They lack data, however, on recovery during the initial stages of TKA post operative recovery, a period when patients are most vulnerable to functional impairments, pain, and difficulty resuming daily activities. While a 2024 prospective study reported significantly improved early outcomes in the SV group compared to MPP at 1 and 3 months, it did not include continuous or real-time data within the first 30 days post-op, leaving this gap in our understanding of recovery during this critical period⁵.

Smart technology, including PIQ can bridge this gap by capturing continuous gait metrics, providing a view of early recovery. Prior studies using external devices (Fary et al., 2023) demonstrated the feasibility of passive gait monitoring but lacked implant-based validation. Persona IQ offers a unique opportunity to directly measure *in vivo* knee kinematics and gait parameters through the recovery period.

Study Design

This is a single-institution, prospective randomized study. Patients of [name], [name], and [name] undergoing primary total knee arthroplasty (TKA) at the Advanced Center for Joint Surgery (Sandy Springs, GA; Cumming, GA) will be screened for eligibility and approached during their pre-operative clinic visits. We plan to enroll 100-120 eligible once obtaining informed consent. For two weeks prior to surgery, enrolled patients will be asked to track their step count using the built-in iPhone Health application. If a patient routinely wears an Apple Watch or similar device, the step count data from the watch may also populate the iPhone Health application and will therefore contribute to the recorded step count. Patients will self-report their average daily step count on the day of surgery by showing the data from the application to research fellows. While recording step count, adherence will be recorded as the number of days with available iPhone Health data meeting validity criteria (≥ 500 steps). Days with 0–499 steps will not be considered valid unless the patient attests to medically-indicated low activity, in which the reason will be documented.

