During surgery, all patients will receive a Zimmer Persona IQ utilizing a medial congruent bearing with a posterior cruciate ligament (PCL) sacrifice. All patellas will be resurfaced as well. This standardized implant choice was made to reduce variability and allow for direct comparison of functional outcome between surgical approaches. PIQ data will be accessed using the Canary Medical database. Patients will be followed for a minimum of 6 months post-operatively, during which they will complete digital patient-reported outcomes.

The surgical approach, MPP or SV, will be randomly assigned with an equal chance of receiving either. This randomization will be stratified by sex and age.

Inclusion Criteria:

- All patients older than 18 years of age who plan to undergo medial congruent polyethylene bearing primary TKA with a PIQ
- Eligible for both approaches
- Have an iPhone and willing to “wear” it for two weeks preoperatively to get an estimated average stepcount

- Provide informed consent
- Willing to complete follow ups

Exclusion Criteria:

- Patients with TKA revisions
- Patients with insufficient pre-operative range of motion in the operative knee (flexion contracture of > 20 degrees or < 90° of knee flexion)
- Patients with Contralateral TKA within study time frame
- Patients with TKA other than medial congruent polyethylene bearing
- Patients with bilateral surgery
- Patients without a valid and active email address
- Patients not willing or able to participate in study and follow-ups
- Patients who use assisted devices to ambulate
- Rheumatoid arthritis

Primary outcomes:

- Preoperative data
 - Preoperative goniometric functional range of motion
 - Step count
 - Pre-Operative Step Count via Force Therapeutics
 - In cases where pre-operative step count is missing or incomplete, patients can update force or discuss what range of activity they are classified in based on step count
- Continuous PIQ Data
 - Tibial ROM
 - Cadence
 - Walking speed
 - Stride length
 - Step count
 - Distance
- 6 week follow up data
 - Goniometric functional range of motion

Secondary outcomes:

- Time to achieving key milestones in daily activities (e.g. ability to perform basic household tasks such as taking out the trash)
- Veterans Rand 12-Item (VR-12) Health Survey (Preop, 6 weeks, 6 months)
- Procedure Satisfaction (6 weeks, 6 months)

- Numeric Pain Rating Scale (NPRS) (Force data)

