- KOOS, JR. (Knee injury and Osteoarthritis Outcome Score for Joint Replacement) - Preop, 6 weeks, and 6 months
- Forgotten Joint Score - Preop, 6 weeks, 6 months

Other measures:

- Patient Demographics including
 - Age
 - Sex
 - Body Mass Index (BMI)
 - American Society of Anesthesiologists (ASA) score
- Surgical side (L/R)
- Comorbidities

ANALYSIS

Post-operative functional data will be extracted from the Canary Medical platform for all Persona IQ participants. Preoperative step count will be collected from each participant's iPhone. Descriptive and comparative statistical analyses will be conducted using this real-time data.

[figure not shown]
Data are broken down descriptively first to understand the distribution of the medial parapatellar and subvastus groups. Continuous data are presented as mean (standard deviation) and categorical data are presented as cell count (%). Shapiro-Wilks and Kolmogorov-Smirnov tests are used to assess the normality of the continuous data. T-tests are used to calculate P values for continuous data and Chi-squared tests are used to calculate P values for categorical data. Following this, an unadjusted and adjusted logistic regression are analyzed using PROMs as the dependent outcome. Significance is determined at P value < .05. All statistical analyses are done using R Studio (version 4.3.1, Vienna, Austria). Using a significance level of 5%, a power of 80% and an effect size of 0.3, we believe that 55-60 patients are needed for the MPP group and 55-60 patients are needed for the SV group to determine a difference of 1000 steps per day.

CONSENT PROCEDURE

Subjects will be identified via the surgical schedule and contacted during their pre-operative clinic visits. A research coordinator will explain the study and obtain informed consent. No study activities (e.g., device usage or data collection) will begin prior to consent. Patients may withdraw at any time.

COST AND COMPENSATION

As this is currently standard of care at Northside Hospital, no compensation will be given.

CONFIDENTIALITY OF DATA

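### The only test the protocol names that fits step count, its main primary outcome, is an unadjusted t-test, so pre-operative step count and the sex and age strata do not enter that comparison

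*Protocol*

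**What the plan says.** The protocol's Introduction states: "The main primary outcome of this study will be step count". The hypothesis there concerns post-operative days 1 to 30.

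The Analysis section names these group comparisons:

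- For single variables: "T-tests are used to calculate P values for continuous data and Chi-squared tests are used to calculate P values for categorical data".
- After that, "an unadjusted and adjusted logistic regression are analyzed using PROMs as the dependent outcome".

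The covariates of the adjusted logistic model are not listed. No ANCOVA, linear regression, mixed model or stratified test is named for step count.

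Two sources of explanatory information are planned:

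- **Pre-operative step count.** Under Study Design, for the two weeks before surgery, "enrolled patients will be asked to track their step count using the built-in iPhone Health application". The Analysis section repeats: "Preoperative step count will be collected from each participant's iPhone". Where the value is missing or incomplete, the Primary outcomes list says "patients can update force or discuss what range of activity they are classified in based on step count".
- **Stratification factors.** Under Study Design: "This randomization will be stratified by sex and age".

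**The concern.** Step count is continuous and is not a patient-reported outcome, so the t-test is the only named method that fits it. The protocol does plan adjustment, but attaches it to outcomes it lists as secondary. The main primary outcome gets the less efficient analysis.

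Patients differ widely in habitual activity. Whatever part of post-operative step count can be predicted from pre-operative activity, sex and age stays in the error term of a t-test. The estimated difference in steps per day is then less precise than the collected data allow. Stratifying the randomisation by prognostic factors and then ignoring them also makes the t-test somewhat conservative, because the arms are balanced on those factors but the standard error does not reflect it.

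**Working it through.** **Inputs from the protocol (Analysis, Study Design).** Significance level 5%, power 80%, effect size 0.3, difference of 1000 steps per day, 55–60 patients per arm, planned enrolment 100–120 (so 50–60 per arm), equal allocation.

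**Assumptions.** Two-sided test; 0.3 read as a standardised mean difference d; one mean daily step count per patient. The correlation r between pre-operative and post-operative step count is not in the protocol. I use 0.3 to 0.7 as the main range and also show 0.1 and 0.2.

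**The plan's own figure.** With d = 0.3, 80% power by the noncentral t needs 176 per arm, not 55–60. The stated sample size does not reproduce. That is a separate problem, but it means power at the stated effect size is already low.

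**Implied standard deviation.** 1000 / 0.3 = 3333 steps per day.

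**Effect of adjusting for baseline.** The residual SD is SD × √(1 − r²), so the effective standardised difference is 0.3 / √(1 − r²): 0.314 at r = 0.3, 0.346 at r = 0.5, 0.420 at r = 0.7. Power is from the noncentral t with noncentrality d_eff × √(n/2). Degrees of freedom are 2n − 2 unadjusted and 2n − 3 with the baseline covariate.

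| r | 60 per arm | 55 per arm | 50 per arm |
|---|---|---|---|
| t-test | 37.1% | 34.5% | 31.8% |
| 0.1 | 37.4% | 34.7% | 32.0% |
| 0.2 | 38.4% | 35.6% | 32.9% |
| 0.3 | 40.1% | 37.3% | 34.4% |
| 0.5 | 46.9% | 43.7% | 40.3% |
| 0.7 | 62.6% | 58.8% | 54.8% |

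**Precision at 60 per arm.** The 95% CI half-width is t(0.975, 118) × 3333 × √(1 − r²) × √(2/60).

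- Unadjusted: 1.980 × 3333 × 0.1826 = 1205 steps per day, wider than the 1000-step target difference.
- r = 0.1 / 0.2: 1199 / 1181.
- r = 0.3 / 0.5 / 0.7: 1150 / 1044 / 861.

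**Equivalent number of patients.** The multiplier 1 / (1 − r²) is 1.10, 1.33 and 1.96 at r = 0.3, 0.5 and 0.7, i.e. 10%, 33% or 96% more patients under the t-test for the same precision.

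**Ignoring the strata.** If sex and age explain a share R² of the variance, the nominal 5% t-test has a true size of about 2 × [1 − Φ(1.96 / √(1 − R²))]. With assumed R² of 0.05 this is 2 × [1 − Φ(2.011)] = 4.4%; with 0.10 it is 2 × [1 − Φ(2.066)] = 3.9%.

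**Simulation check.** Settings were 60 per arm, four sex-by-age strata and blocks of 4 (both assumed), and 8000 runs per setting. The t-test's type I error was 0.046–0.050 with non-prognostic strata and 0.034–0.046 at R² = 0.10; ANCOVA gave 0.045–0.056. Power at r = 0.3 / 0.5 / 0.7 with non-prognostic strata was 0.37 / 0.36 / 0.38 for the t-test and 0.39 / 0.46 / 0.62 for ANCOVA, in line with the formula.

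**What adjustment cannot do.** Reaching 80% power at d = 0.3 would need r of about 0.81 at 60 per arm, 0.83 at 55 or 0.85 at 50.

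**The case against.** **The covariates may be left to an SAP, and the t-test sentence may describe only a table of group comparisons.** The sentence follows the descriptive statistics and does not name step count, and the same section speaks generally of comparative analyses. An SAP that is not at hand could add an adjusted model. This is fair as a caution. But the protocol does state a method for continuous data and does say where adjustment applies, and step count is not there. The criticism is of that stated choice.

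**The information does not go wholly unused.** Pre-operative step count is listed among the outcomes, sex and age are used in the randomisation, and all three could enter the logistic model. This stands. The claim is limited to the step-count comparison.

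**The t-test is valid.** This stands. With one value per patient it keeps type I error at or below 5%, and the estimate is not biased.

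**r may be small.** Baseline comes from a phone, a watch or an activity range, and the outcome from an implant soon after surgery. This limits the gain: at r of 0.2 or less it is about one percentage point, and the doubling of effective sample size needs r near 0.7. It is no argument against adjusting, because a weak baseline covariate costs about one degree of freedom out of roughly 118.

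**The low power belongs to the sample-size problem.** Largely true. If the real effect were d = 0.52, roughly what 55–60 per arm can detect, power at 60 per arm would be about 81% unadjusted and 84% at r = 0.3. The relative gain in precision, 1 / (1 − r²), does not depend on d.

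**Conclusion.** The concern holds. For its main primary outcome the protocol names only an unadjusted test, and it reserves adjustment for patient-reported outcomes. This is a loss of efficiency in a valid analysis, so it should be changed but does not undermine the trial.

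At d = 0.3 and 60 per arm the forgone power is about 3, 10 or 26 percentage points at r = 0.3, 0.5 or 0.7, and about 1 point or less below that. The likely value may sit at the low end because the two step counts come from different devices. These figures rest on the assumed r, on a two-sided test, and on reading 0.3 as a standardised difference with an implied SD of 3333. The conservatism figures rest on an assumed R² of 5–10% for sex and age. The sample-size mismatch remains whichever analysis is chosen.

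**What to change.** In the Analysis section, state the step-count analysis explicitly:

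- **Model.** ANCOVA on each patient's mean daily implant step count over post-operative days 1 to 30, with surgical approach as the factor and pre-operative step count, sex and age as covariates. A mixed model with a patient random effect and the same single average contrast would serve equally.
- **Use of baseline.** Enter the pre-operative value only as a covariate. Do not analyse change from baseline, because baseline and outcome are measured by different devices.
- **Missing baseline.** Fix one rule in advance for patients with only an activity range, for example mean imputation with a missing-baseline indicator, so that no randomised patient is dropped.
- **Sensitivity.** Keep the unadjusted t-test on patient means.

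The cost is a few sentences and minor programming. The covariates are already planned to be collected, apart from exact step counts in patients on the activity-range fallback, and patients bear no extra burden. Naming the covariates before outcome data are seen also prevents a later choice among models.

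### The hypothesis concerns speed of recovery over days 1-30, but the only test fixed for daily step count is a t-test with no time term and no defined per-patient summary

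*Protocol*

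**What the plan says.** The INTRODUCTION sets an aim about the course of recovery: the implant data are to show "their recovery trajectories during the first 30 days post-operatively". The hypothesis reads: "We hypothesize that the SV approach will demonstrate a quicker return to functional milestones in the early post-operative period compared to the MPP approach". It adds that better gait metrics, step count among them, are expected "from post-op day 1 to 30 in the SV group compared to the MPP group". It then states: "The main primary outcome of this study will be step count".

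The REVIEW OF LITERATURE justifies the trial by noting that earlier comparisons reported outcomes only at separate time points.

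The ANALYSIS section names these methods:
- For continuous variables: "T-tests are used to calculate P values for continuous data".
- For categorical variables: chi-squared tests.
- One regression, which is not for step count: "an unadjusted and adjusted logistic regression are analyzed using PROMs as the dependent outcome".

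It gives no per-patient summary of the daily step series. The sample-size sentence speaks of a difference of 1000 steps per day without naming a day or window. Time to reaching milestones of daily living is listed under Secondary outcomes, also without a matching method.

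**The concern.** A two-sample t-test takes one number per patient. The protocol does not say how thirty daily counts become that number. Its only stated target, a difference in steps per day, describes a level. A higher level and a faster recovery are different things, and a comparison of levels does not separate them.

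Three things are at stake. The daily series, which is the reason for using the implant, would be collapsed or left to a choice of day or window made after the data are seen. An advantage confined to the early days would be diluted if the number chosen is the 30-day mean, and missed altogether if it is a late day. And because steps rise during recovery, a simple mean over available days depends on which days a patient has.

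**Working it through.** **Inputs from the protocol (ANALYSIS).** Significance level 5% (taken as two-sided), power 80%, effect size 0.3 (taken as Cohen's d), difference 1000 steps/day, 55-60 per arm. No SD is given; 1000/0.3 implies 3333.

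**Inputs assumed.** The shape of the SV advantage over time, the correlation between a patient's days, and the SDs of slope and of day-to-day variation. The protocol gives none of these.

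**Formula.** Power comes from the noncentral t distribution with 2n − 2 degrees of freedom and noncentrality (difference/SD) × √(n/2).

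**1. The protocol's own figure.** At d = 0.3, n = 2 × (1.960 + 0.842)² / 0.3² ≈ 175 per arm (176 with the exact t-test), not 55-60. At 55-60 per arm, power for a constant 1000 steps at SD 3333 is 34-37%. That is a separate problem. It matters here only because low power at SD 3333 is partly due to it, so a second SD is used below. With 55 and 60 per arm, 80% power needs d = 0.539 and 0.516, that is SD = 1000/0.539 = 1855 and 1000/0.516 = 1939.

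**2. A fading advantage tested on the 30-day mean.** Let the advantage on day t be 1000 × (30 − t)/29, from 1000 on day 1 to 0 on day 30. Its mean over the 30 days is 500.
- SD 3333 for the analysed mean: d = 500/3333 = 0.15. With 55 per arm the noncentrality is 0.15 × √27.5 = 0.79 and power is 12.2%. With 60 per arm it is 12.9%.
- SD 1855-1939: the effect is half of what is detectable with 80% power (d about 0.27 or 0.26), and power is 29%.

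**3. The same fade with other per-patient numbers.** Here the SD is that of a single day, and days are correlated within patient, either equally (0.5 or 0.7) or by AR(1) with 0.9. The week-1 mean difference is 1000 × 26/29 = 897 steps. Power at 55-60 per arm:

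| Number entered in the t-test | Daily SD 3333 | Daily SD 1926 |
|---|---|---|
| 30-day mean | 15-23% | 36-56% |
| Week-1 mean | 35-49% | 77-92% |
| Day 30 | 5% | 5% |
| Per-patient slope | 18% to over 99% | 43% to over 99% |

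The low slope figures come from AR(1) 0.9 and the high ones from equal correlation. A 2-degree-of-freedom test of arm plus arm-by-day ranges from 31% to over 99% at SD 3333.

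**4. Slope test with between-patient slope variation.** The slope difference is 1000/29 = 34.5 steps/day per day, and the sum of squared deviations of days 1-30 is 2247.5. With day-to-day SD 1500, the SD of a patient's slope is √(slope SD² + 1500²/2247.5). For slope SDs of 40, 70, 100 and 130 and 55 per arm, power is 94, 65, 40 and 27% if daily residuals are independent, but 53, 40, 29 and 22% if they follow AR(1) with 0.9.

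**5. Direction of the slope.** In this scenario SV starts higher and the arms meet, so SV has the flatter line: SV minus MPP (medial parapatellar) = −34.5. If SV instead started level and rose faster, the sign would be positive. The sign alone does not identify quicker recovery.

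**6. Missing days.** If steps rise in a straight line from 500 to 4500, a patient without days 1-7 has an available-day mean 483 steps/day above the full 30-day mean. For a rise from 1000 to 3000 the excess is 241.

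**The case against.** A reader might infer that the trial cannot test quicker recovery at all. The documents do not support that. A t-test on a prespecified slope, week-1 mean or number of days to a step threshold tests speed or early benefit, and the protocol does not exclude these. What is wrong is that it names none of them and states its target as a level.

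A reader might also take the closing of the gap within the month as part of the hypothesis. It is not. The protocol uses long-term for 6 months and beyond, expects better gait metrics throughout days 1 to 30, and cites a study with SV benefit at 1 and 3 months. If the advantage is constant, a comparison of 30-day means is a sound test and nothing is lost.

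The power figures rest on assumed SDs and correlations, and working steps 3 and 4 show how far they move. A time term is therefore no promise of high power. The missing-day excess biases the comparison between arms only if missingness differs between arms, and the protocol gives no reason to expect that.

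Finally, a longitudinal model is often left to the SAP, which is not at hand, so its absence alone would be no finding. But the protocol does not defer the method: it fixes t-tests for continuous data, and a SAP that followed it would carry the mismatch forward. The secondary time-to-milestone outcome does not close the gap, since it is not step count and no method listed is meant for it.

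**Conclusion.** The point holds as a mismatch between hypothesis and test: a question about speed and trajectory is paired with a time-blind test on an undefined summary of daily data. The size depends on facts the protocol does not give. Under a straight-line fade to zero by day 30, the t-test on the 30-day mean has about 12% power at the implied SD and 29% at the more favourable SD, if those are SDs of the 30-day mean. If they are single-day SDs, the range is 15-56%. These figures illustrate the dilution; they do not predict the result. It should be corrected before analysis.

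**What to change.** Replace the t-test for implant step count, and likewise for walking speed and range of motion, with a linear mixed model on daily values for days 1-30. Include arm, day (categorical or spline) and arm-by-day, with a prespecified covariance that allows for day-to-day autocorrelation.

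- Keep the model-based mean difference over days 1-30 as the single deciding contrast. With complete data it has the same target as a t-test on the 30-day mean and gains no power over it, but it is less sensitive to which days are missing.
- Test quicker recovery with a joint test of arm and arm-by-day, read together with prespecified early-window contrasts, for example week by week. Do not rest it on the sign of a linear arm-by-day slope.

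The cost is protocol wording and a little more analysis work, with no further patients or data. The day function and covariance must be fixed in advance.

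### Logistic regression is fixed for PROMs that are mostly numeric scores, with no binary outcome defined and no ordinal model named

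*Protocol*

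**What the plan says.** After the descriptive summaries and simple tests, the ANALYSIS section states that "an unadjusted and adjusted logistic regression are analyzed using PROMs as the dependent outcome". It does not say whether this is binary or ordinal, and it defines no responder, threshold or change criterion for any PROM.

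Other parts of the protocol bear on this:

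- **Secondary outcomes** lists "KOOS, JR. (Knee injury and Osteoarthritis Outcome Score for Joint Replacement) - Preop, 6 weeks, and 6 months" and "Forgotten Joint Score - Preop, 6 weeks, 6 months". It also lists VR-12 at the same three times, NPRS from Force with no times given, and Procedure Satisfaction at 6 weeks and 6 months with no scale given.
- **INTRODUCTION** states the hypothesis as "improved gait metrics (ROM, step count, walking speed) and PROMs". That is a direction of change, not a responder rate.
- **ANALYSIS**, same paragraph: continuous data are summarised by mean and SD, and "T-tests are used to calculate P values for continuous data".
- **Study Design**: "This randomization will be stratified by sex and age" and "We plan to enroll 100-120 eligible once obtaining informed consent", which is 50 to 60 per arm at equal allocation.

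**The concern.** Logistic regression without a qualifier normally means a model for a yes/no outcome. The PROMs are mostly scores, so the model named does not fit the data listed. An analyst following the text has to cut each score, and the protocol fixes no cut.

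Two things are at stake.

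- **Precision.** The logistic regression is the only adjusted PROM analysis in the protocol. Pre-operative KOOS JR, VR-12 and Forgotten Joint Score values are collected, and sex and age are stratification factors. Adjusting for these should sharpen the comparison; cutting the score first gives away more than the adjustment recovers in most realistic cases.
- **What is estimated.** The t-test gives a difference in means and the binary model an odds ratio at a cut. The adjusted result would not be an adjusted version of the unadjusted one. A cut that is not fixed beforehand could also be chosen after the data are seen.

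**Working it through.** **Inputs from the protocol.** 50 to 60 per arm (100-120 enrolled, 1:1); significance level 5%, taken as two-sided because sidedness is not stated. There is no PROM effect size, SD, distribution or cut, so there is no PROM figure to reproduce. The 55-60 per arm in ANALYSIS is for step count, and this point does not rest on it.

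**Assumptions.** Scores roughly normal with equal SDs; true difference d = 0.5 SD; pre/post correlation r = 0.3 to 0.5. The value 0.5 is close to what 60 per arm can detect with 80% power: (1.960 + 0.842) × √(2/60) = 0.51 SD. Results for d = 0.3 are in step 2.

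**Step 1. Information kept by a cut.** Relative efficiency of a cut at quantile q, with c the normal deviate and φ the normal density, is φ(c)² / [q(1 − q)].

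| Cut | φ(c)² / [q(1 − q)] | Efficiency |
|---|---|---|
| Median | 0.1592 / 0.25 | 0.637 |
| 30th or 70th percentile | 0.1209 / 0.21 | 0.576 |
| 20th or 80th percentile | 0.0784 / 0.16 | 0.490 |

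With 120 patients, a median cut leaves the information of about 0.637 × 120 = 76 patients, and an 80/20 cut that of about 0.490 × 120 = 59.

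**Step 2. Unadjusted power, closed form.** For the full score, the normal approximation is Φ(d/√(2/n) − 1.96). At n = 60 this is Φ(0.5/0.1826 − 1.96) = Φ(0.78) = 0.78; the t-test value is 0.775.

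Cutting at the control-arm median gives proportions of 0.500 and 0.691 above the cut. Cutting at the control-arm 80th percentile gives 0.200 and 0.366. The two-proportion test then has:

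| Case | t-test | Median cut | 80th percentile cut |
|---|---|---|---|
| d = 0.5, 60 per arm | 0.775 | 0.572 | 0.525 |
| d = 0.5, 50 per arm | 0.697 | 0.496 | 0.454 |
| d = 0.3, 60 per arm | 0.371 | 0.253 | 0.221 |

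**Step 3. Adjusted against adjusted.** Both models include the baseline score. For ANCOVA the residual variance falls by the factor 1 − r². The closed form at n = 60 gives:

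- r = 0.3: Φ(2.739/√0.91 − 1.96) = Φ(0.91) = 0.82
- r = 0.5: Φ(2.739/√0.75 − 1.96) = Φ(1.20) = 0.885

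Simulation with d = 0.5 (4,000 runs per case, Monte Carlo SE at most 0.8 points) gives:

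| Case | ANCOVA | Binary logistic, median cut | Binary logistic, 80th percentile cut |
|---|---|---|---|
| 60 per arm, r = 0.3 | 0.80 | 0.58 | 0.55 |
| 60 per arm, r = 0.5 | 0.88 | 0.66 | 0.60 |
| 50 per arm, r = 0.3 | 0.74 | 0.52 | 0.47 |
| 50 per arm, r = 0.5 | 0.81 | 0.57 | 0.50 |
| 60 per arm, r = 0.5, score capped at +1 SD | 0.83 | 0.64 | 0.58 |

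Rejection rates under the null are 0.049 to 0.056 for every test, so the issue is precision, not false positives.

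**Step 4. If ordinal was meant.** A Wilcoxon test, as a stand-in for an ordinal model without covariates, has power 0.75-0.76 at 60 per arm, against 0.77-0.78 for the t-test in the same runs. Almost nothing is lost.

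**The case against.** The strongest reply is that responder thresholds, covariates and the exact form of the model are ordinary content for a statistical analysis plan, which was not available. With pre-stated responders or an ordinal form, the sentence could be carried out as it stands. Missing cuts or covariates alone would indeed be no finding. But the protocol does not leave the model open: it names a family that, read plainly, does not suit most of the outcomes listed. A later plan would have to cut the scores or read the sentence in a way it does not state.

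Other points stand as limits:

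- If ordinal regression was intended, the loss nearly vanishes and only the wording needs attention.
- The t-test appears to keep a valid full-score comparison in a randomised trial, with about 78% power at 60 per arm under the same assumption. Reporting a mean difference and an odds ratio side by side is not in itself an error.
- Procedure Satisfaction has no stated scale and may suit a logistic model. VR-12 is listed as a survey, so that it is scored numerically is likely but not stated.
- The 0.5 SD effect is assumed. At 0.3 SD all methods are weak and the absolute loss is smaller (37% against 25% or 22%, unadjusted).
- The adjusted binary model is less powerful than the unadjusted t-test for correlations up to about 0.7. Near 0.8 the median-cut model draws level (81% against 79% at d = 0.5). ANCOVA remains clearly better than either.
- The hypothesis refers to days 1 to 30, whereas KOOS JR, VR-12 and the Forgotten Joint Score are collected post-operatively at 6 weeks and 6 months. Changing the model does not resolve that.

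**Conclusion.** The point holds. The protocol commits its only adjusted PROM analysis to a model that, read as binary, does not match outcomes that are mostly numeric scores. In the normal-score cases calculated, the cost is roughly a third to a half of the information in each score. That is about 20 to 31 percentage points of power against ANCOVA at d = 0.5 and r = 0.3 to 0.5, with 50 to 60 per arm.

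The mismatch is read directly from the text. The size rests on assumed effect, correlation, distribution and cut points, and on the binary reading. It should be corrected, but it touches secondary outcomes only: the step-count analysis, the sample size and the unadjusted t-tests are not affected.

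**What to change.** Replace the logistic regression sentence in ANALYSIS with the following content:

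- **Main PROM analysis:** linear regression (ANCOVA) of each PROM score on surgical approach, adjusted for sex, age and the pre-operative score where collected. Report the adjusted mean difference with its 95% confidence interval as the main PROM result.
- **Times:** 6 weeks and 6 months for KOOS JR, VR-12 and the Forgotten Joint Score; for NPRS, the times at which it is actually recorded in Force.
- **Skewed or bounded scores, and Procedure Satisfaction if it is a rating:** a proportional-odds model, named as such. If ordinal regression was what the sentence meant, say so by name.
- **Binary logistic regression:** supplementary only, for a responder outcome defined before the data are seen.

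The cost is the wording of one sentence. Data, visits and software stay the same.
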